9.7.1.8.3 LABORATORY VALUES

Laboratory results will be summarized using International System of Units, as appropriate. For all quantitative parameters listed in [Section 9.5.1.5.3](#), the actual value and the change from baseline to each postbaseline visit and to the end of treatment (defined as the last on-treatment value) will be summarized by visit and treatment group using descriptive statistics. Qualitative parameters listed in [Section 9.5.1.5.3](#) will be summarized using frequencies (number and percentage of subjects), and changes from baseline to each postbaseline visit and to end of treatment will be reported using shift tables. Percentages will be based on the number of subjects with both nonmissing baseline and relevant postbaseline results.

Laboratory test results will be assigned a low/normal/high (LNH) classification according to whether the value was below (L), within (N), or above (H) the laboratory parameter's reference range. Within-treatment comparisons for each laboratory parameter will be based on 3-by-3 tables (shift tables) that compare the baseline LNH classification to the LNH classification at each postbaseline visit and at the end of treatment. Similar shift tables will also compare the baseline LNH classification to the LNH classification for the highest and lowest value during the Treatment Period.

[Appendix 1](#) (Sponsor's Grading for Laboratory Values) presents the criteria that will be used to identify subjects with treatment-emergent markedly abnormal laboratory values (TEMAVs). Except for phosphate, a TEMAV is defined as a postbaseline value with an increase from baseline to a Grade of 2 or higher. For phosphate, a TEMAV was defined as a postbaseline value with an increase from baseline to a Grade of 3 or higher. When displaying the incidence of TEMAVs, each subject may be counted once in the laboratory parameter high and in the laboratory parameter low categories, as applicable.

Lymphocyte subsets measured (including but not limited to CD4 [T helper cells], CD8 [cytotoxic T cells], CD19 [B cells], CD16/CD56 [natural killer cells] and CD14 [macrophages] and regulatory T cells) will be summarized in the same manner as other laboratory parameters. Mean lymphocyte subsets and the mean change from baseline in lymphocyte subsets will also be displayed graphically over time by dose.

Serum IgG, IgM, and IgA will be measured and summarized in the same manner as other laboratory parameters.

9.7.1.8.4 VITAL SIGNS

Descriptive statistics for vital signs parameters (ie, systolic and diastolic BP, pulse, respiratory rate, temperature, weight), and changes from baseline will be presented by visit and treatment group.

9.7.1.8.5 ELECTROCARDIOGRAMS

Descriptive statistics for ECG parameters and changes from baseline will be presented by visit and treatment group. Shift tables will present changes from baseline in ECG interpretation (categorized as normal; abnormal, not clinically significant; and abnormal, clinically significant) to the end of treatment.

In addition, the number (percentage) of subjects with at least 1 postbaseline abnormal ECG result in QTcF during the Treatment Period will be summarized. Clinically abnormal ECG results in QTcF will be categorized as follows:

Absolute QTc interval prolongation:

- QTc interval >450 msec
- QTc interval >480 msec
- QTc interval >500 msec

Change from baseline in QTc interval:

- QTc interval increases from baseline >30 msec
- QTc interval increases from baseline >60 msec

9.7.1.8.6 OTHER SAFETY ANALYSES

Cognitive decline will be assessed as a safety assessment, in addition to efficacy assessments. Cognitive assessments will include CBB ([Section 9.7.1.6](#)). (revised per Amendment 05)

9.7.2 Determination of Sample Size

A total of 15 subjects per dose group is deemed sufficient to derive adequate safety and PK/PD data to aid in the selection of appropriate doses and the design of the Phase 3 studies that may be planned subsequently. (revised per Amendment 05)

9.7.3 Interim Analysis

In order to make decisions about the remainder of the study as well as the full elenbecestat clinical development program, the sponsor will unblind safety, PK, and PD data on an ongoing basis and perform interim analyses of these data. Investigators, other clinical site staff, subjects, caregivers/informants, and study team will remain blinded to study treatment. (revised per Amendments 03 and 05)

An interim safety analysis will also be conducted when all subjects have completed 12 weeks of treatment (or discontinue study drug early). (revised per Amendments 01, 03, 04, and 05)

9.7.4 Other Statistical/Analytical Issues

Stratification (revised per Amendment 01)

Within the 2 clinical cohorts (MCI/Prodromal and mild to moderate AD), subjects will be stratified at randomization by *ApoE4* status (positive or negative) and prior treatment with AChEIs or memantine or both (yes or no). (revised per Amendment 01)

9.7.5 Procedure for Revising the Statistical Analysis Plan

If the SAP needs to be revised after the study starts, the sponsor will determine how the revision impacts the study and how the revision should be implemented. The details of the revision will be documented and described in the clinical study report.

11 PROCEDURES AND INSTRUCTIONS (ADMINISTRATIVE PROCEDURES)

11.1 Changes to the Protocol

Any change to the protocol requires a written protocol amendment or administrative change that must be approved by the sponsor before implementation. Amendments specifically affecting the safety of subjects, the scope of the investigation, or the scientific quality of the study require submission to health or regulatory authorities as well as additional approval by the applicable IRBs/IECs. These requirements should in no way prevent any immediate action from being taken by the investigator, or by the sponsor, in the interest of preserving the safety of all subjects included in the study. If the investigator determines that an immediate change to or deviation from the protocol is necessary for safety reasons to eliminate an immediate hazard to the subjects, the sponsor's medical monitor and the IRB/IEC for the site must be notified immediately. The sponsor must notify the health or regulatory authority as required per local regulations.

Protocol amendments that affect only administrative aspects of the study may not require submission to health or regulatory authority or the IRB/IEC, but the health or regulatory authority and IRB/IEC (or if regionally required the head of the medical institution) should be kept informed of such changes as required by local regulations. In these cases, the sponsor may be required to send a letter to the IRB/IEC and the Competent Authorities (or, if regionally required, the head of the medical institution) detailing such changes.

11.2 Adherence to the Protocol

The investigator will conduct the study in strict accordance with the protocol (refer to ICH E6, Section 4.5).

11.3 Monitoring Procedures

The sponsor's or CRO's CRA will maintain contact with the investigator and designated staff by telephone, letter, or email between study visits. Monitoring visits to each site, and potential remote source document verification, will be conducted by the assigned CRA as described in the monitoring plan. The investigator (or if regionally required, the head of the medical institution) will allow the CRA to inspect the clinical, laboratory, and pharmacy facilities to assure compliance with GCP and local regulatory requirements. The eCRFs and subject's corresponding original medical records (source documents) are to be fully available for review by the sponsor's representatives at regular intervals. These reviews verify adherence to study protocol and data accuracy in accordance with local regulations. All records at the site are subject to inspection by the local auditing agency and to IRB/IEC review.

In accordance with ICH E6, Section 1.52, source documents include, but are not limited to, the following:

- Clinic, office, or hospital charts
- Copies or transcribed health care provider notes that have been certified for accuracy after production
- Recorded data from automated instruments such as IxRS, x-rays, and other imaging reports (eg, sonograms, computed tomography scans, MRIs, radioactive images, ECGs, rhythm strips, electroencephalography, polysomnographs, pulmonary function tests) regardless of how these images are stored, including microfiche and photographic negatives
- Pain, quality of life, or medical history questionnaires completed by subjects
- Records of telephone contacts
- Diaries or evaluation checklists
- Drug distribution and accountability logs maintained in pharmacies or by research personnel
- Laboratory results and other laboratory test outputs (eg, urine pregnancy test result documentation and urine dip-sticks)
- Correspondence regarding a study subject's treatment between physicians or memoranda sent to the IRBs/IECs
- CRF components (eg, questionnaires) that are completed directly by subjects and serve as their own source

11.4 Recording of Data

An eCRF is required and must be completed for each subject by qualified and authorized personnel. All data on the eCRF must reflect the corresponding source document, except when a section of the eCRF itself is used as the source document. Any correction to entries made on the eCRF must be documented in a valid audit trail where the correction is dated, the individual making the correction is identified, the reason for the change is stated, and the original data are not obscured. Only data required by the protocol for the purposes of the study should be collected.

The investigator must sign each eCRF. The investigator will report the eCRFs to the sponsor and retain a copy of the eCRFs.

11.5 Identification of Source Data

All data to be recorded on the eCRF must reflect the corresponding source documents.

11.6 Retention of Records

The circumstances of completion or termination of the study notwithstanding, the investigator (or if regionally required, the head of the medical institution or the designated representative) is responsible for retaining all study documents, including but not limited to the protocol, copies of eCRFs, the Investigator's Brochure, and regulatory agency registration documents (eg, Form FDA 1572, ICFs, and IRB/IEC correspondence). The site should plan to retain study documents, as directed by the sponsor, for at least 2 years after the last approval of a marketing application in an ICH region and until there are no pending or contemplated marketing applications in an ICH region or at least 3 years have elapsed since the formal discontinuation of clinical development of the investigational product.

It is requested that at the completion of the required retention period, or should the investigator retire or relocate, the investigator contact the sponsor, allowing the sponsor the option of permanently retaining the study records.

11.7 Auditing Procedures and Inspection

In addition to routine monitoring procedures, the sponsor's Clinical Quality Assurance department conducts audits of clinical research activities in accordance with the sponsor's standard operating procedures to evaluate compliance with the principles of ICH GCP and all applicable local regulations. If a government regulatory authority requests an inspection during the study or after its completion, the investigator must inform the sponsor immediately.

11.8 Handling of Study Drug

All study drugs will be supplied to the principal investigator (or a designated pharmacist) by the sponsor. Drug supplies must be kept in an appropriate secure area (eg, locked cabinet) and stored according to the conditions specified on the drug labels. The investigator (or a designated pharmacist) must maintain an accurate record of the shipment and dispensing of the study drug in a drug accountability ledger, a copy of which must be given to the sponsor at the end of the study. An accurate record of the date and amount of study drug dispensed to each subject must be available for inspection at any time. The CRA will visit the site and review these documents along with all other study conduct documents at appropriate intervals once study drug has been received by the site.

All drug supplies are to be used only for this study and not for any other purpose. The investigator (or site personnel) must not destroy any drug labels or any partly used or unused drug supply before approval to do so by the sponsor. At the conclusion of the study and as appropriate during the study, the investigator (or a designated pharmacist) will return all used and unused drug containers, drug labels, and a copy of the completed drug disposition form to the sponsor's CRA (or designated contractor).

11.9 Publication of Results

All manuscripts, abstracts, or other modes of presentation arising from the results of the study must be reviewed and approved in writing by the sponsor in advance of submission pursuant to the terms and conditions set forth in the executed CTA between the sponsor/CRO and the institution/investigator. The review is aimed at protecting the sponsor's proprietary information existing either at the date of the commencement of the study or generated during the study. The detailed obligations regarding the publication of any data, material results, or other information generated or created in relation to the study shall be set out in the agreement between each investigator and the sponsor or CRO, as appropriate.

11.10 Disclosure and Confidentiality

The contents of this protocol and any amendments and results obtained during the study should be kept confidential by the investigator, the investigator's staff, and the IRB/IEC and will not be disclosed in whole or in part to others, or used for any purpose other than reviewing or performing the study, without the written consent of the sponsor. No data collected as part of this study will be used in any written work, including publications, without the written consent of the sponsor. These obligations of confidentiality and non-use shall in no way diminish such obligations as set forth in either the Confidentiality Agreement or CTA executed between the sponsor/CRO and the institution/investigator. All persons assisting in the performance of this study must be bound by the obligations of confidentiality and non-use set forth in either the Confidentiality Agreement or CTA executed between the institution/investigator and the sponsor/CRO.

11.11 Discontinuation of Study

The sponsor reserves the right to discontinue the study for medical reasons or any other reason at any time. If a study is prematurely terminated or suspended, the sponsor will promptly inform the investigators/institutions and regulatory authorities of the termination or suspension and the reason(s) for the termination or suspension. The IRB/IEC will also be informed promptly and provided the reason(s) for the termination or suspension by the sponsor or by the investigator/institution, as specified by the applicable regulatory requirement(s).

The investigator reserves the right to discontinue the study should his/her judgment so dictate. If the investigator terminates or suspends a study without prior agreement of the sponsor, the investigator should inform the institution where applicable, and the investigator/institution should promptly inform the sponsor and the IRB/IEC and provide the sponsor and the IRB/IEC with a detailed written explanation of the termination or suspension. Study records must be retained as noted above.

11.12 Subject Insurance and Indemnity

The sponsor will provide insurance for any subjects participating in the study in accordance with all applicable laws and regulations.

12 APPENDICES

Appendix 1 Sponsor's Grading for Laboratory Values

(revised per Amendment 01)

| | Grade 1 | Grade 2 | Grade 3 | Grade 4 |
|--|---|---|---|---|
| BLOOD/BONE MARROW | | | | |
| Hemoglobin (conversion from g/dL×0.6206) | Female (ULN = 15.9 g/dL) <11.1 – 10.0 g/dL <111 – 100 g/L <6.9 – 6.2 mmol/L Male (ULN = 17.7 g/dL) <12.6 – 10.0 g/dL <126 – 100 g/L <7.8 – 6.2 mmol/L | <10.0 – 8.0 g/dL <100 – 80 g/L <6.2 – 4.9 mmol/L | <8.0 g/dL <80 g/L <4.9 mmol/L; transfusion indicated | life-threatening consequences; urgent intervention indicated |
| Leukocytes (total white blood cell) | <3.40 – 3.0×10 ⁹ /L <3.40 10 ³ /uL – 3000/mm ³ (ULN = 10.80 10 ³ /μL) | <3.0 – 2.0×10 ⁹ /L <3000 – 2000/mm ³ | <2.0 – 1.0×10 ⁹ /L <2000 – 1000/mm ³ | <1.0×10 ⁹ /L <1000/mm ³ |
| Lymphocytes | not applicable | <700 – 500/mm ³ <0.7 – 0.5×10 ⁹ /L | <500 – 200/mm ³ <0.5 – 0.2×10 ⁹ /L | <200/mm ³ <0.2×10 ⁹ /L |
| Neutrophils | not applicable | <1.4 – 1.0×10 ⁹ /L <1400 – 1000/mm ³ | <1.0 – 0.5×10 ⁹ /L <1000 – 500/mm ³ | <0.5×10 ⁹ /L <500/mm ³ |
| Platelets | <155 – 75.0×10 ⁹ /L <155 10 ³ /uL – 75,000/mm ³ (ULN = 379 10 ³ /μL) | <75.0 – 50.0×10 ⁹ /L <75,000 – 50,000/mm ³ | <50.0 – 25.0×10 ⁹ /L <50,000 – 25,000/mm ³ | <25.0×10 ⁹ /L <25,000/mm ³ |
| METABOLIC/LABORATORY | | | | |
| Albumin, serum- low (hypoalbuminemia) | 2 - 59 years (ULN = 5.5 g/dL) <3.5 – 3 g/dL <35 – 30 g/L 59 - 69 years (LLN-ULN) <3.6 g/dL – 3 g/dL 69 - 79 years (LLN-ULN) <3.5 g/dL – 3 g/dL 79 - 89 years (LLN-ULN) <3.5 g/dL – 3 g/dL | <3 – 2 g/dL <30 – 20 g/L | <2 g/dL <20 g/L | life-threatening consequences; urgent intervention indicated |
| Alkaline phosphatase | Female: 18 - 19 years >101 – 3.0×101 19 - 61 years ULN=107 61 - 71 years ULN=112 71 - 150 years ULN=108 Male 18 - 19 years >127 – 3.0×127 19 - 61 years ULN=102 61 - 71 years ULN=103 71 - 150 years ULN=105 | >3.0 – 5.0×ULN See previous column for ULN values | >5.0 – 20.0×ULN See previous column for ULN values | >20.0×ULN See previous column for ULN values |
| Alanine aminotransferase | Female: >32 – 3.0×32 | Female: >3.0 – 5.0×32 | Female: >5.0 – 20.0×32 | Female: >20.0×32 |

| | Grade 1 | Grade 2 | Grade 3 | Grade 4 |
|---|--|--|---|---|
| | Male: >44 – 3.0 x 44 | Male >3.0 – 5.0x44 | Male: >5.0 – 20.0x44 | Male: >20.0x44 |
| Aspartate aminotransferase | >40 – 3.0x40 | >3.0 – 5.0x40 | >5.0 – 20.0x40 | >20.0x40 |
| Bilirubin (hyperbilirubinemia) | >1.2 – 1.5x1.2 | >1.5 – 3.0x1.2 | >3.0 – 10.0x1.2 | >10.0x1.2 |
| Calcium, serum-low (hypocalcemia) (conversion to mmolx0.25) | <8.5 – 8.0 mg/dL <2.13 – 2.0 mmol/L | <8.0 – 7.0 mg/dL <2.0 – 1.75 mmol/L | <7.0 – 6.0 mg/dL <1.75 – 1.5 mmol/L | <6.0 mg/dL <1.5 mmol/L |
| Calcium, serum-high (hypercalcemia) | >10.6 – 11.5 mg/dL >2.65 – 2.9 mmol/L | >11.5 – 12.5 mg/dL >2.9 – 3.1 mmol/L | >12.5 – 13.5 mg/dL >3.1 – 3.4 mmol/L | >13.5 mg/dL >3.4 mmol/L |
| Cholesterol, serum-high (hypercholesterolemia) (conversion to mmol/L x0.02586) | 0 - 19 years >169 – 300 mg/dL >4.37 – 7.75 mmol/L 19 - 150 years >199 – 300 mg/dL >5.15 – 7.75 mmol/L | >300 – 400 mg/dL >7.75 – 10.34 mmol/L | >400 – 500 mg/dL >10.34 – 12.92 mmol/L | >500 mg/dL >12.92 mmol/L |
| Creatinine | Female >1.00 mg/dL – 1.5x1.00 Male >1.27 mg/dL – 1.5x1.27 | Female >1.5 – 3.0x1.00 Male >1.5 mg/dL – 3.0x1.27 | Female >3.0 – 6.0x1.00 Male >3.0 mg/dL – 6.0 x1.27 | Female >6.0x1.00 Male >6.0x1.27 |
| Gamma glutamyl transpeptidase | Female >60 IU/L – 3.0x60 Male >65 IU/L – 3.0x65 | Female >3.0 – 5.0x60 Male >3.0 – 5.0x65 | Female >5.0 – 20.0x60 Male >5.0 – 20.0x65 | Female >20.0x60 Male >20.0x65 |
| Glucose, serum-high (hyperglycemia) (conversion to mmol/L x0.0555) | Fasting glucose value >99 – 160 mg/dL >5.5 – 8.9 mmol/L | Fasting glucose value >160 – 250 mg/dL >8.9 – 13.9 mmol/L | >250 – 500 mg/dL; >13.9 – 27.8 mmol/L; hospitalization indicated | >500 mg/dL; >27.8 mmol/L; life-threatening consequences |
| Glucose, serum-low (hypoglycemia) | <65 – 55 mg/dL <3.6 – 3.0 mmol/L | <55 – 40 mg/dL <3.0 – 2.2 mmol/L | <40 – 30 mg/dL <2.2 – 1.7 mmol/L | <30 mg/dL <1.7 mmol/L life-threatening consequences; seizures |
| Phosphate, serum-low (hypophosphatemia) (conversion to mmol/L x0.323) | not applicable | <2.5 – 2.0 mg/dL <0.8 – 0.6 mmol/L | <2.0 – 1.0 mg/dL <0.6 – 0.3 mmol/L | <1.0 mg/dL <0.3 mmol/L life-threatening consequences |
| Potassium, serum-high (hyperkalemia) | not applicable | >5.5 – 6.0 mmol/L | >6.0 – 7.0 mmol/L hospitalization indicated | >7.0 mmol/L life-threatening consequences |
| Potassium, serum-low (hypokalemia) | <3.5 mEq/L – 3.0 mmol/L | <LLN – 3.0 mmol/L; symptomatic; intervention indicated | <3.0 – 2.5 mmol/L hospitalization indicated | <2.5 mmol/L life-threatening consequences |
| Sodium, serum-high (hypernatremia) | >144 mEq/L – 150 mmol/L | >150 – 155 mmol/L | >155 – 160 mmol/L hospitalization indicated | >160 mmol/L life-threatening consequences |
| Sodium, serum-low (hyponatremia) | <134 mEq/L – 130 mmol/L | Not applicable | <130 – 120 mmol/L | <120 mmol/L life-threatening consequences |
| Triglyceride, serum-high (hypertriglyceridemia) | 150 – 300 mg/dL 1.71 – 3.42 mmol/L | >300 – 500 mg/dL >3.42 – 5.7 mmol/L | >500 – 1000 mg/dL >5.7 – 11.4 mmol/L | >1000 mg/dL >11.4 mmol/L life-threatening consequences |

| | Grade 1 | Grade 2 | Grade 3 | Grade 4 |
|---------------------------------------|--|----------------|--|--|
| Uric acid, serum-high (hyperuricemia) | Female >7.1 – 10 mg/dL Male >8.6 – 10 mg/dL Both ≤0.59 mmol/L without physiologic consequences | Not applicable | Female >7.1 – 10 mg/dL Male >8.6 – 10 mg/dL Both ≤0.59 mmol/L without physiologic consequences | >10 mg/dL >0.59 mmol/L life-threatening consequences |

LLN = lower limit of normal, ULN = upper limit of normal.

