9.5.1.5.3 LABORATORY MEASUREMENTS

Clinical laboratory tests to be performed, including hematology, chemistry, urinalysis, and CSF are summarized in [Table 4](#). Subjects should be in a seated or supine position during blood collection. [Table 6](#), [Table 7](#), and [Table 14](#) show the visits and time points at which blood for clinical laboratory tests and urine for urinalysis will be collected in the study. (revised per Amendment 07)

See [Section 9.3.3](#) for safety criteria for discontinuation from study drug-related to absolute counts of CD4, CD8, and B lymphocytes, and for lymphocyte subset counts. See [Appendix 6](#) for safety criteria for discontinuation from study drug related to absolute lymphocyte counts.

Table 4 Clinical Laboratory Tests

| Category | Parameters |
|-----------------------------|--|
| Hematology | Hematocrit, hemoglobin, platelets, red blood cell count, and white blood cell count with differential (bands, basophils, eosinophils, lymphocytes, monocytes, neutrophils). PT, PTT, and INR (Screening, Baseline, and Visit 21 only) (revised per Amendment 02 and 07) |
| Chemistry | |
| Electrolytes | Bicarbonate, calcium, chloride, phosphate, potassium, sodium |
| Liver function tests | Alanine aminotransferase, alkaline phosphatase, aspartate aminotransferase, gamma glutamyl transpeptidase, direct bilirubin, total bilirubin |
| Renal function tests | Blood urea/blood urea nitrogen, creatinine |
| Other | Albumin, cholesterol, globulin, glucose, lactate dehydrogenase, total protein, triglycerides, uric acid |
| Urinalysis | Bacteria, casts, crystals, epithelial cells, glucose, ketones, occult blood, pH, protein, red blood cells, specific gravity, white blood cells |
| Other | Lymphocyte T and B cell subset analyses (see Table 5). Regulatory T cells (revised per Amendment 04) PBMCs (revised per Amendment 02) Ig analyses (IgG, IgA, and IgM). Viral screen (HCVAb [Hepatitis C] and HbsAg [Hepatitis B]). Viral characterization (including HSV1, HSV2 and CMV, etc.) Serum pregnancy test (females of child bearing potential only) Tuberculosis Interferon Gamma Release Assays Tests for thyroid function (thyroid stimulating hormone, free triiodothyronine and free thyroxin) and vitamin B12 Blood sample for storage for subsequent testing of immune status Cerebrospinal fluid sampling |

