- s: Site staff will contact the subject or the caregiver or informant the day before the PK blood sampling to provide instructions that subjects must not take their study drug at home on the day of the PK blood sampling. During this telephone contact with the subject or the caregiver or informant, the site staff should document the time that the subject took their study drug that day, ie, the day before the PK blood sampling.
- t: Two plasma PK samples will be obtained: one at predose (trough) and another 1 to 6 hours postdose at Visit 5, Visit 11, Visit 14, and Visit 16 and 4 to 8 hours postdose at Visit 7 and Visit 18 (or ED). Therefore, subjects or their caregivers or informants must be instructed not to take their study drug at home on the day the PK sampling is performed. Instead, subjects will take the study drug at the clinic after collection of the predose PK sample. At Visit 7 and Visit 18 (or ED) the PK blood sample should be collected shortly before or shortly after completing the LP. If at an ED Visit, the subject has already stopped study drug, then no dosing will take place, but the trough PK sample will still be collected, followed by LP at approximately the same time as at previous visits. A second PK blood sample will be collected as close as possible to the LP, either shortly before or shortly after the LP. (revised per Amendment 01)
- u: PD and exploratory biomarker blood samples should be collected at fasting or at least 2 hours after the most recent meal and, as far as is feasible, samples should be taken at the same time of day. At Visits 5, 11, 14, and 16 the PD blood samples should be collected predose.

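### Grade 2 high-glucose TEMAVs use a fasting limit, but the protocol neither requires fasting for chemistry samples nor asks for fasting status to be recorded

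*Protocol*

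**What the plan says.** **Grading.** In the high-glucose row of Appendix 1, Grade 1 (>99–160 mg/dL) and Grade 2 carry the label "Fasting glucose value". The Grade 2 cell reads "Fasting glucose value >160 – 250 mg/dL >8.9 – 13.9 mmol/L". The Grade 3 cell reads ">250 – 500 mg/dL; >13.9 – 27.8 mmol/L; hospitalization indicated" and, like Grade 4 (>500 mg/dL), has no fasting label. The low-glucose row has none at any grade.

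**Use of the grades.** Section 9.7.1.8.3 applies this table: "Except for phosphate, a TEMAV is defined as a postbaseline value with an increase from baseline to a Grade of 2 or higher".

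**Samples.** Table 4 in Section 9.5.1.5.3 puts glucose in the chemistry panel: "Albumin, cholesterol, globulin, glucose, lactate dehydrogenase, total protein, triglycerides, uric acid". The collection condition given there concerns posture only: "Subjects should be in a seated or supine position during blood collection". Tables 6, 7 and 14 and their footnotes add no meal condition for chemistry.

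**Meal conditions elsewhere.** The protocol does set them for other samples. Footnote u to Table 7 says "PD and exploratory biomarker blood samples should be collected at fasting or at least 2 hours after the most recent meal". Similar conditions apply to baseline PK and PD blood (Table 6), to CSF, and to Extension Phase PD blood (Table 14, footnote p).

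**Role.** Laboratory parameters belong to the primary endpoint of the Core Study (Section 9.7.1.1.1) and of the Extension Phase (Appendix 6). Safety data are summarised descriptively (Section 9.7.1.8).

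**The concern.** A limit defined for fasting glucose is used to flag markedly abnormal values in samples whose fasting status is not controlled and, as far as the protocol goes, not recorded. Applied as written, the TEMAV rule can count a reading between 160 and 250 mg/dL taken after a meal as a treatment-emergent marked abnormality. The error can also run the other way: a non-fasting baseline reading already in that band would hide a later genuine rise to Grade 2.

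Such readings are plausible in any arm, because the exclusion criteria remove only diabetes that is not well controlled. What is at stake is the interpretability of one laboratory line in the safety tables, most of all in the Extension Phase, where there is no concurrent arm to compare with.

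**Working it through.** The protocol gives no figure to reproduce here, so the check sets sampling rules against grading rules and counts visits.

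**1. Where the TEMAV starts.** The rule needs Grade 2 or higher, and Grade 2 high glucose starts above 160 mg/dL. The units agree: 160 × 0.0555 = 8.88 and 250 × 0.0555 = 13.88 mmol/L, against the stated 8.9 and 13.9. The threshold itself is not mistyped. What is open is which samples it fits.

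**2. Core Study, on treatment (Table 7).**
- Chemistry: Visits 5, 7, 9, 11, 14, 15, 16, 17, 18, which is 9 visits.
- PD blood, under the fasting-or-two-hours condition: Visits 5, 7, 11, 14, 16, 18, which is 6 of the 9.
- No meal condition on any blood sample: Visits 9, 15, 17, so 9 − 6 = 3.
- Fasting required for chemistry: 0 of 9. Two hours after a meal is not fasting, and the condition is written for the PD tube, not the chemistry tube.

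**3. Extension Phase, treatment period (Table 14 and Appendix 6 text).**
- Chemistry: every visit from 21 to 38, which is 18 visits.
- PD blood: Visits 21 (or 20), 28, 32, 35 and 38, which is 5.
- No parallel meal condition: 18 − 5 = 13 visits.

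**4. Weight of one subject.** The target is about 60 randomised (±20%) over 4 arms, that is 15 per arm with a range of 12 to 18. One subject is 1/15 = 6.7 percentage points (1/12 = 8.3; 1/18 = 5.6).

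**5. Illustration only.** The protocol gives no rate of non-fasting readings above 160 mg/dL. *Assume* a probability q per visit that a draw exceeds the limit only because of a meal, independent across the 9 on-treatment Core visits, in a subject whose baseline is below Grade 2. The chance of at least one such reading is 1 − (1 − q)^9:

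| q per visit | Subjects with at least one | Expected of 15 |
|---|---|---|
| 1% | 8.6% | 1.3 |
| 2% | 16.6% | 2.5 |
| 5% | 37.0% | 5.6 |

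The range shows how repeated sampling accumulates. It is not an estimate for this trial.

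**The case against.** **Only part of the row is affected.** Grades 3 and 4 have no fasting label and still meet the TEMAV rule, and samples that happen to be fasting can be graded as intended. This stands. It limits the point to readings of >160–250 mg/dL.

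**The error is the same in every blinded arm.** Sampling conditions do not depend on treatment, the summary is descriptive, and glucose is one parameter among many. For Core between-arm comparisons this largely stands. It gives no protection in the single-arm Extension Phase, whose primary endpoint includes clinical laboratory tests.

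**On PK days the dose with food follows the predose sample.** That is correct, but it protects only the predose tube. PD blood must be predose at Visits 5, 11, 14 and 16, not at 7 or 18. Nothing ties the chemistry tube to the predose draw at any visit.

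**The laboratory manual, requisition or SAP may deal with it.** None is shown, so fasting status may in fact be recorded. The protocol cites the laboratory manual for PK and biomarker samples, but Section 9.5.1.5.3 does not cite it for safety chemistry. A SAP can say how non-fasting values are graded only if the status was captured.

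**Inferences to avoid.** A reader might infer that on-treatment shifts are biased upward because baseline is fasting and later draws are fed. The documents do not support this: the PD meal condition is the same before and after baseline, the preference for a fasting lumbar puncture also applies at Visits 7 and 18, and CSF sampling is voluntary. A reader might also infer that subjects at Visits 9, 15 and 17 had already dosed at home with food. Core dosing is once daily with food at no fixed clock time, and at Visits 15 and 17 cognitive testing should come before blood draws, so a recent meal is not established.

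**Conclusion.** The mismatch holds and is minor. The entry point for a high-glucose TEMAV is a fasting limit, while the protocol neither requires fasting for clinical chemistry nor calls for fasting status to be recorded with it. Grade 2 high-glucose counts may therefore include meal effects. None of the 9 on-treatment Core chemistry visits requires fasting; 3 of those 9, and 13 of 18 Extension Phase treatment visits, have no parallel meal condition on any blood sample.

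It would go too far to call the hyperglycaemia TEMAV counts invalid or to say that no sample can be graded: values above 250 mg/dL, hypoglycaemia grades and fasting samples are untouched. No hypothesis test or sample size depends on the count. How many readings are affected cannot be derived from the protocol. The conclusion assumes that no document outside it already requires or records fasting for chemistry.

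**What to change.** - Record time of last meal, or fasting yes/no, with every chemistry sample in the Core Study and the Extension Phase.
- Apply the Grade 1–2 high-glucose limits to fasting samples only.
- Keep Grades 3–4 for all samples, as the table now reads.
- Tabulate non-fasting values of >160–250 mg/dL as a separate line rather than dropping them.
- If the laboratory requisition already captures fasting status, cite it in Section 9.5.1.5.3 and use it in the TEMAV rule. For samples already drawn without it, show Grade 2 readings as fasting status unknown.

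The cost is one data field and one condition in the TEMAV program, plus fewer samples gradable at Grade 2. Treatment and subject management are not affected.
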